**Possible**

Adverse events that, after careful medical evaluation, do not meet the criteria for a probable relationship to the non-standard of care procedure, but for which a connection cannot be ruled out with certainty. The following characteristics will apply:

- The event occurs after non-standard of care procedure, and
- The event is not a known reaction to non-standard of care procedure, but cannot be explained by a commonly occurring alternative etiology

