**Probable**

Adverse events that, after careful medical evaluation, are considered with a high degree of certainty to be related to the proposed follow-up imaging and blood draw studies that are non standard of care.

The following characteristics will apply:

- A reasonable temporal relationship exists between the event and the procedure, and
- The event is a known reaction to the non-standard of care procedure, which can be explained by an alternative etiology commonly occurring in the population/individual, or
- The event is not a known reaction to the proposed non-standard of care procedure but cannot be reasonably explained by an alternative etiology.

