### Unlikely

Adverse events that, after careful medical evaluation, do not meet the criteria for a possible or probable relationship to non-standard of care procedure for which a connection is unlikely. The following characteristics will apply:

- The event does not follow a reasonable temporal sequence from administration of the non-standard of care procedure, or
- May have been produced by environmental factors, and there is no apparent pattern of response to the non-standard of care procedure.

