### *Reporting of Serious Adverse Events*

All investigators conducting the clinical study supported by the NHLBI must report both expected (protocol-defined) and unexpected serious adverse events. All serious adverse events must be reported as dictated by the specific IRB policy. Deaths unrelated to study participation will be reported to the IRB at the time of continuing review. Deaths related to study participation and associated with the non-standard of care procedures will be promptly reported to the IRB. The PI will notify the NHLBI program officer of any unexpected serious adverse events via e-mail within 24 hours of receipt of the event.

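### The three causality grades are not exhaustive and partly out of order: a well-timed event with a common alternative cause can fit no grade, while an unexplained, badly timed one is graded Possible

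*Combined protocol and SAP*

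**What the plan says.** Section 12.0 (definitions subsection, numbered 11.1) asks the investigator to relate each adverse event to the study's non-standard of care assessments, using three grades. Each has a lead-in and a list of characteristics that are said to apply.

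- **Probable.** Timing: "A reasonable temporal relationship exists between the event and the procedure, and" one of two further bullets must hold. The first concerns any "known reaction to the non-standard of care procedure, which can be explained by an alternative etiology commonly occurring in the population/individual, or". The second, its alternative, concerns whatever is "not a known reaction to the proposed non-standard of care procedure but cannot be reasonably explained by an alternative etiology".
- **Possible.** The lead-in covers events that "do not meet the criteria for a probable relationship to the non-standard of care procedure, but for which a connection cannot be ruled out". Two characteristics follow: the event need only come after the procedure; in addition, "The event is not a known reaction to non-standard of care procedure, but cannot be explained by a commonly occurring alternative etiology".
- **Unlikely.** The lead-in covers events that meet neither of the other grades. Then either "The event does not follow a reasonable temporal sequence from administration of the non-standard of care procedure", or the event may be environmental with no pattern of response.

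There is no fourth grade. The same subsection makes relatedness to a non-standard of care study intervention part of the definition of an adverse event. Under Reporting of Serious Adverse Events, unrelated deaths wait for continuing review, while "Deaths related to study participation and associated with the non-standard of care procedures will be promptly reported to the IRB".

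**The concern.** A causality scale should give every event one grade, and a closer link to the procedure should never give a lower grade. Two features of the wording work against that.

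First, the second bullet of Possible is almost the last bullet of Probable. Both demand an event that is not a known reaction and lacks another explanation. The ordinary middle case is an event soon after a study procedure that could also come from the patient's own disease, and neither grade admits it when it is not a known reaction. All participants have cardiomyopathy and at least moderate mitral regurgitation, so such alternatives can be expected to arise.

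Second, Possible drops the requirement of reasonable timing and asks only for sequence. That lets in unexplained events whose timing is implausible.

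At stake are whether an event is recognised as an adverse event under the protocol's own definition, and how fast a death reaches the IRB.

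**Working it through.** There is no figure to reproduce, so the check is logical. For events after the procedure, take four properties from the three definitions: reasonable timing or not; known reaction or not; alternative cause none, uncommon only, or common; and environmental with no pattern of response or not (possible only where an alternative exists).

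Cells: 2 (timing) × 2 (known) × [1 (no alternative) + 2 × 2 (uncommon or common, environmental or not)] = 2 × 2 × 5 = 20.

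**Rules as printed**

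- Probable = timing AND [(known AND common alternative) OR (not known AND no alternative of any kind)].
- Possible = not Probable AND after the procedure AND not known AND no common alternative.
- Unlikely = neither of these AND (no reasonable timing OR environmental without pattern).

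**Reasonable timing, environmental bullet not applying**

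| Known reaction | Alternative cause | As printed | With 'cannot' in the second bullet of Probable |
|---|---|---|---|
| Yes | None | No grade | Probable |
| Yes | Uncommon only | No grade | Probable |
| Yes | Common | Probable | No grade |
| No | None | Probable | Probable |
| No | Uncommon only | Possible | Possible |
| No | Common | No grade | No grade |

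Ungraded: 3 of 6 as printed, 2 of 6 with 'cannot'. The other 14 of the 20 cells always get a grade, because timing is not reasonable or the environmental bullet applies.

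The last row is the gap tied to the wording of Possible. It fails the third bullet of Probable because an alternative exists, the second bullet of Possible because that alternative is common, and both bullets of Unlikely. It stays ungraded with 'can' or 'cannot', whether or not the timing bullet of Probable governs both later bullets, and whether or not the two etiology phrases are taken as equivalent.

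The first two rows are ungraded only because of 'can'. Changing it to 'cannot' and nothing else closes them but opens the third row.

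**What Possible adds beyond Probable.** Read literally, 5 of the 20 cells. Four also have an Unlikely characteristic: three lack reasonable timing, and one is well timed with an uncommon, environmental cause. The fifth is the fifth row of the table, which has no Unlikely characteristic. If the two etiology phrases are treated as equivalent, Possible adds one cell: not known, no alternative, no reasonable timing.

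**Order.** That badly timed, unexplained event is graded Possible. If the timing bullet of Probable is read as governing only the known-reaction bullet, the same event becomes Probable, which is further out of order.

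**The case against.** **Possible has content of its own.** A reader might infer that it is empty, or adds only events that also meet Unlikely. The documents do not support that. Probable excludes events with any reasonable alternative etiology; Possible excludes only those with a common one. A well-timed, not-known event with only an uncommon, non-environmental alternative is Possible and nothing else.

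**No event receives two grades.** The lead-in to Unlikely excludes anything that meets Possible or Probable. The overlap is in characteristics only.

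**Part of the gap has another source.** The ungraded known-reaction rows come from 'can' in Probable, not from the wording of Possible. Environmental causes with no pattern of response also provide a route to Unlikely for some events.

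**Judgement may fill the gap.** Grading follows medical evaluation, and the lead-in to Possible, a connection that cannot be excluded, suits the middle case. This stands only in part: the protocol then says the listed characteristics will apply, and the second bullet rules that case out.

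**Reporting is less exposed than it looks.** A reader might infer that serious events would go unreported, or that ungraded events would be handled as unrelated. The reporting subsection does not name the three grades. It requires expected and unexpected serious adverse events to be reported and sends unexpected ones to the NHLBI program officer within 24 hours, without reference to the grade. How ungraded events would be handled is not stated.

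These points limit the consequence. They do not close the gap.

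**Conclusion.** The concern holds in a limited form. The grades are not exhaustive, and they are partly out of order. A well-timed event that is not a known reaction and has a common, non-environmental alternative cause has no grade under every reading tested. A well-timed known reaction with no alternative cause also has none as printed, and correcting that one word alone moves the gap to well-timed known reactions with a common alternative. An unexplained event without reasonable timing is meanwhile graded Possible.

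The size is 3 of 6 well-timed, non-environmental cases as printed and 2 of 6 with 'cannot'. These are combinations of criteria, not a forecast of how many events are affected. That depends on which reactions count as known and how often patients have another explanation.

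The conclusion assumes that the listed characteristics bind, as the protocol says. The effect is confined to safety classification: what counts as an adverse event, and the IRB timing of death reports. No endpoint, sample size or error rate is touched.

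**What to change.** Revise the three definitions together:

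1. **Probable.** Resolve 'can' or 'cannot' in the second bullet, and say that the timing requirement governs both later bullets.
2. **Possible.** Require reasonable timing, failure to meet Probable, and an alternative cause, common or not, that could also explain the event, whether or not it is a known reaction.
3. **Unlikely.** Keep it for events without reasonable timing, and say how its environmental bullet ranks against Possible. Without a ranking the existing lead-in would give precedence to Possible, and with 'cannot' in Probable the bullet would decide no well-timed event.
4. **Reporting.** State which grades count as related for the death-reporting rule, in line with IRB policy.

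Checked against the table: with 'cannot' and the restated Possible, the rows from top to bottom become Probable, Probable, Possible, Probable, Possible, Possible, so 0 of 6 are ungraded. Events without reasonable timing all fall to Unlikely. If 'can' were kept, the first row would still be ungraded (1 of 6), so restating Possible alone is not enough. Keeping the restriction to common alternatives in Possible would leave the fifth row ungraded, a gap that does not exist now.

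The cost is a few lines in one protocol section and a matching change to the adverse event form. The small downside is that somewhat more events will be graded Possible.

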### Unlikely

Adverse events that, after careful medical evaluation, do not meet the criteria for a possible or probable relationship to non-standard of care procedure for which a connection is unlikely. The following characteristics will apply:

- The event does not follow a reasonable temporal sequence from administration of the non-standard of care procedure, or
- May have been produced by environmental factors, and there is no apparent pattern of response to the non-standard of care procedure.

### *Reporting of Serious Adverse Events*

All investigators conducting the clinical study supported by the NHLBI must report both expected (protocol-defined) and unexpected serious adverse events. All serious adverse events must be reported as dictated by the specific IRB policy. Deaths unrelated to study participation will be reported to the IRB at the time of continuing review. Deaths related to study participation and associated with the non-standard of care procedures will be promptly reported to the IRB. The PI will notify the NHLBI program officer of any unexpected serious adverse events via e-mail within 24 hours of receipt of the event.

### ***Specific Adverse Event Definitions***

Bleeding: A bleeding event is defined by any one of the following:

- Transfusion of > 10 unit's RBC within the first 24 hours following surgery
- Death due to hemorrhage
- Re-operation for hemorrhage or tamponade

NOTE: Hemorrhagic stroke is considered a neurological event and not as a separate bleeding event.

Cardiac Arrhythmias: Any documented arrhythmia that *results in clinical compromise* (e.g., hemodynamic compromise, oliguria, pre-syncope or syncope) that requires hospitalization or requires a physician visit or occurs during a hospital stay. Cardiac arrhythmias are classified as one of two types:

- Sustained ventricular arrhythmia requiring defibrillation or cardioversion
- Sustained supraventricular arrhythmia requiring drug treatment or cardioversion

Pericardial Fluid Collection: Intervention or percutaneous catheter drainage. This event will be subdivided into those with clinical signs of tamponade (e.g. increased central venous pressure and decreased cardiac output) and those without signs of tamponade.

Hepatic Dysfunction: An increase in any two of the following hepatic laboratory values (total bilirubin, aspartate aminotransferase/AST and alanine aminotransferase/ALT) to a level greater than three times the upper limit of normal for the hospital, (or if hepatic dysfunction is the primary cause of death).

**Major Infection:** A new clinical infection accompanied by pain, fever, drainage and/or leukocytosis that is treated by anti-microbial agents (non-prophylactic). A positive culture from the infected site or organ should be present unless strong clinical evidence indicates the need for treatment despite negative cultures. The general categories of infection are listed below:

- **Localized Infection:** Infection localized to any organ system or region (e.g. mediastinitis) without evidence of systemic involvement (see sepsis definition), ascertained by standard clinical methods and either associated with evidence of bacterial, viral, fungal or protozoal infection, and/or requiring empirical treatment.
- **Endocarditis:** Signs, symptoms, and laboratory findings consistent with endocarditis, including but not limited to fever  $\geq 38.0^{\circ}\text{C}$ , positive blood cultures, new regurgitant murmurs or heart failure, evidence of embolic events (e.g., focal neurologic impairment, glomerulonephritis, renal and splenic infarcts, and septic pulmonary infarcts), and peripheral cutaneous or mucocutaneous lesions (e.g., petechiae, conjunctival or splinter hemorrhages, Janeway lesions, Osler's nodes, and Roth spots). Echocardiographic evidence of a new intra-cardiac vegetation with or without other signs and symptoms should be considered adequate evidence to support the diagnosis of endocarditis. TEE should be the modality of choice for diagnosis of prosthetic valve endocarditis.
- **Sepsis:** Evidence of systemic involvement by infection, manifested by positive blood cultures and/or hypotension.

#### **Myocardial Infarction**

Myocardial infarction (MI) should be classified when there is evidence of myocardial necrosis in a clinical setting consistent with myocardial ischemia. Under these conditions, any one of the following criteria meets the diagnosis for myocardial infarction:

- **Myocardial Infarction**  
Detection of rise and/or fall of cardiac biomarkers (preferably troponin) with at least one value above the 99th percentile of the upper reference limit (URL) together with evidence of myocardial ischemia with at least one of the following:
  - Symptoms of ischemia;
  - ECG changes indicative of new ischemia (new ST-T changes or new left bundle branch block [LBBB]);
  - Development of pathological Q waves in the ECG;
  - Imaging evidence of new loss of viable myocardium or new regional wall motion abnormality.
- **Peri-CABG Myocardial Infarction**  
For CABG in patients with normal baseline troponin values, elevations of cardiac biomarkers above the 99th percentile URL are indicative of peri-procedural myocardial necrosis. By convention, increases in biomarkers  $> 5 \times$  99th percentile URL plus either new pathological Q waves or new LBBB, or angiographically documented new graft of native coronary artery occlusion, or imaging evidence of new loss of viable myocardium have been designated as defining CABG-related MI.

- Peri-Percutaneous Intervention (PCI) Myocardial Infarction

For PCI in patients with normal baseline troponin values, elevations of cardiac biomarkers above the 99th percentile URL are indicative of peri-procedural myocardial necrosis. By convention, increases in biomarkers  $> 3 \times$  99th percentile URL have been designated as defining PCI-related MI. A subtype related to a documented stent thrombosis is recognized. Sudden unexpected cardiac death, involving cardiac arrest, often with symptoms suggestive of myocardial ischemia, and accompanied by presumed new ST elevation or new LBBB, and/or evidence of fresh thrombus by coronary angiography and/or autopsy, with death occurring before blood samples obtained, or at a time before the expected appearance of cardiac biomarkers in blood will be classified as a mortality due to MI.

### Neurologic Dysfunction

Any new, temporary, or permanent, focal or global neurological deficit ascertained by a standard neurological examination (administered by a neurologist or other qualified physician and documented with appropriate diagnostic tests and consultation note). The examining physician will distinguish between a transient ischemic attack (TIA), which is fully reversible within 24 hours (and without evidence of infarction), and a stroke, which lasts longer than 24 hours (or less than 24 hours if there is evidence of infarction). The Modified Rankin Scale and the NIH Stroke Scale must be administered at time of event (within 72 hours following the event) and 90 days following the event to document the presence and severity of neurological deficits.

Each neurological event must be subcategorized as:

- Transient Ischemic Attack defined as an acute event that resolves completely within 24 hours with no imaging evidence of infarction.
- Ischemic or Hemorrhagic Stroke (Cerebrovascular Accident), defined as an event that persists beyond 24 hours or less than 24 hours associated with infarction on an imaging study. Hemorrhagic conversion of an ischemic stroke should be classified as ischemic.
- Toxic Metabolic Encephalopathy defined as a disorder of the brain function that arises from abnormal systemic metabolism or exogenous substances, altering awareness and/or consciousness, in which there is a non-focal neurological examination and a negative brain image.
- Other

### Renal Events

Two categories of renal events will be identified:

- Renal Dysfunction

Abnormal kidney function defined by  $> 100\%$  rise in serum creatinine (Cr) from baseline, and Cr  $> 2.0$

- Renal Failure

New requirement for hemodialysis related to renal dysfunction. This definition excludes aquapheresis for volume removal alone.

### Respiratory Failure

Impairment of respiratory function requiring re-intubation, tracheostomy or the inability to discontinue ventilatory support within 48 hours post-surgical intervention. This excludes intubation for re-operation or temporary intubation for diagnostic or therapeutic procedures.

### Right Heart Failure

Symptoms and signs of persistent right ventricular dysfunction [central venous pressure (CVP) > 18 mmHg with a cardiac index <2.0 L/min/m^2 in the absence of elevated left atrial/pulmonary capillary wedge pressure (> 18 mmHg), tamponade, ventricular arrhythmias or pneumothorax] requiring RVAD implantation, inhaled nitric oxide or inotropic therapy, for a duration of > 7 day.

### Arterial Non-CNS Thromboembolism

An acute systemic arterial perfusion deficit in any non-cerebrovascular organ system due to thromboembolism confirmed by one or more of the following:

- Standard clinical and laboratory testing
- Operative findings
- Autopsy findings

This definition excludes neurological events.

### Venous Thromboembolic Event

Evidence of venous thromboembolic event (e.g. deep vein thrombosis, pulmonary embolism) by standard clinical and laboratory testing.

### Wound Dehiscence

Disruption of the apposed surfaces of a surgical incision, excluding infectious etiology, and requiring surgical repair.

Other An event that causes clinically relevant changes in the patient's health, or any event that is life-threatening, results in a fatality, results in permanent disability, requires hospitalization, or prolongs an existing hospital stay.

**Page intentionally left blank**

**Appendix 1:**  
**New York Heart Association (NYHA) Classification**

# New York Heart Association (NYHA) classification

NYHA grading		MET*
Class I	No limitations. Ordinary physical activity does not cause undue fatigue, dyspnoea or palpitations (asymptomatic LV dysfunction).	>7
Class II	Slight limitation of physical activity. Ordinary physical activity results in fatigue, palpitation, dyspnoea or angina pectoris (mild CHF).	5
Class III	Marked limitation of physical activity. Less than ordinary physical activity leads to symptoms (moderate CHF).	2-3
Class IV	Unable to carry on any physical activity without discomfort. Symptoms of CHF present at rest (severe CHF).	1.6

\*MET (metabolic equivalent) is defined as the resting  $\dot{V}O_2$  for a 40-year-old 70kg man. 1 MET = 3.5ml  $\dot{V}O_2$ /min/kg body weight.

Reproduced from: National Heart Foundation of Australia and the Cardiac Society of Australia and New Zealand (Chronic Heart Failure Guidelines Expert Writing Panel). Guidelines for the prevention, detection and management of chronic heart failure in Australia. Updated October 2011

**Appendix 2:**  
- **Six minute walk test (6MWT) recording form**

(Affix patient label here)

Patient ID:

Family name:

Given name(s):

Date of birth:

Sex:  M  F  I

Heart Education Assessment Rehabilitation Toolkit

## Six Minute Walk Test (6MWT) recording form

- Medical history checked
- Medical clearance provided for the patient to participate in exercise testing

Contraindications to 6MWT:

- Resting heart rate > 120 beats / min after 10 minutes rest (relative contraindication)
- Systolic blood pressure > 180 mm Hg +/- diastolic blood pressure > 100 mm Hg (relative contraindication)
- Resting SpO2 < 85% on room air or on prescribed level of supplemental oxygen
- Physical disability preventing safe performance
- No contraindications identified

6MWT 1						Date:	Time:
Supplemental Oxygen						Mobility Aid	
Time mins	BP	SpO2	HR	RPE	Distance walked	Rests / comments	
Rest							
1							
2							
3							
4							
5							
6							
Recovery 1							
2							
Total distance: _____			Symptom recovery: _____			HR recovery: _____	
Limiting factor: _____							
Was test terminated?  No  Yes If yes: when? _____							
6MWT Termination Criteria:				 Intolerable dyspnoea, unrelieved by rest  Persistent SpO2 <85% (Note: pending clinical presentation)  Abnormal gait pattern (leg cramps, staggering, ataxia)  Other clinically warranted reason			
 Chest pain or angina-like symptoms  Heart rate > Predicted HR max  Evolving mental confusion, light-headedness or incoordination  Physical or verbal severe fatigue							

(Affix patient label here)

Patient ID:

Family name:

Given name(s):

Date of birth:

Sex:  M  F  I

